8.4 Demographic and Baseline Disease Characteristics

Demographics and baseline disease characteristics summaries will be provided for the Safety Population. Patient demographics, including age (in years) at consent, race, ethnicity, baseline body mass index (BMI) (in kg/m²), and baseline body surface area (BSA) (in m²), will be summarized using descriptive statistics. Age as a categorical variable (< 65 or ≥ 65 years) will also be summarized.

The following conversions and equations will be used as applicable:

- Height (in cm) = height (in inches) × 2.54
- Weight (in kg) = weight (in lbs) × 0.4536
- BMI (kg/m²) = weight (kg) ÷ (height (m)²)
- BSA (m²) = $\sqrt{[(\text{height (cm)} \times \text{weight (kg)}) \div 3600]}$

Disease characteristics at baseline will be summarized using descriptive statistics and will include the following:

- ECOG performance status at baseline

- time from initial diagnosis of cancer (in months)
- metastatic disease site
- TNM classification at diagnosis
- received bisphosphonates
- pharmacologically castrate (yes/no)
- surgically castrate (yes/no)
- sum of target lesions per RECIST 1.1 at baseline (mm)
- baseline predictive laboratory tests including testosterone, alkaline phosphatase, PSA, LDH, and hemoglobin

Prior cancer therapy at screening will be summarized using descriptive statistics and will include the following:

- total number of prior systemic therapies
- prior systemic therapies by category
 - next generation AR
 - ADT
 - Immunotherapy
 - Immune checkpoint inhibitor
 - Chemotherapy in the hormone-sensitive setting
 - Chemotherapy in the castrate-resistant setting
 - Any chemotherapy
 - Bone-targeted therapy
 - PSMA targeted
 - PARP inhibitor
 - TKI
 - Radiopharmaceutical
 - Other
- best response to most recent systemic therapy
- prior radiation therapy (yes/no) and type
- prior cancer surgery (yes/no) and type

8.5 Medical History

General medical and surgical history will be provided in a by-patient data listings only.

8.6 Prior and Concomitant Medication

All medications will be coded to WHO Drug Dictionary Anatomical Therapeutic Chemical (ATC) classification and preferred name ([WHO-DDE B3](#)). At the time of database lock, the latest version of WHO-DDE will be used to code all medications. The WHO-DDE version

number will be reported in footnotes in the concomitant medication listing and described in the study report.

Prior medications are those received before the first dose of study drug or who have a partial date that suggests the drug was begun prior to the first dose of study drug. Concomitant medications are those received at any point after first dose of study drug. Pre-dose medications are those prescribed in the protocol to be received by the patient prophylactically prior to administration of HPN424. These include dexamethasone, diphenhydramine, acetaminophen, non-steroidal anti-inflammatories, and anti-emetics. All medications reported on the pre-med CRF will be included as pre-dose medications.

Prior and concomitant medication data, including pre-meds, will be provided in by-patient data listings only.

9 EFFICACY

All efficacy data will be reported only in by-patient data listings.

Best overall response (BOR), progression-free survival (PFS), overall survival (OS), duration of response (DOR), and change from baseline in PSA are all secondary endpoints for Part 2 Dose Escalation. Duration of disease control (DODC) is an additional exploratory endpoint for this study.

All efficacy endpoints derived from tumor imaging and response assessments are determined by the investigator using Prostate Cancer Working Group Criteria 3 (PCWG3). Evaluations of overall response are identified as complete response (CR), partial response (PR), stable disease (SD), progressive disease (PD), or not evaluable (NE).

9.1 Efficacy Endpoints

9.1.1 Best Overall Response (BOR)

A patient's BOR is defined as the best disease response assessed during the study given a hierarchy of overall response results (CR > PR > SD > PD > NE). BOR will be based on assessments collected after the first dose of study drug until disease progression is documented. Assessments collected after the start of new cancer treatment will not be considered.

Confirmation of a response is not required for BOR. Patients who do not have post-baseline assessments will be considered non-responders.

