10.8 Analysis of Efficacy

Preliminary analysis of efficacy of HPN424 will be based on radiographic response per Prostate Cancer Working Group 3 (PCWG3) criteria (see the guidelines in [Appendix 6](#)).

Efficacy Endpoint Definitions:

- Objective Response Rate (ORR), defined as the proportion of patients who achieve a CR or PR determined by the investigator according to the PCWG3 criteria
- Progression-free Survival (PFS), defined as the time from first receipt of HPN424 to documented disease progression or death due to any cause, whichever occurs first (summarized descriptively using Kaplan Meier method)
- Duration of Response (DOR), defined as the time from the first observed response (CR or PR) to documented disease progression or death due to any cause (summarized descriptively using Kaplan Meier method)
- Overall Survival (OS), defined as the time from first receipt of HPN424 to death due to any cause (summarized descriptively using Kaplan Meier method)

Primary efficacy analyses will measure overall response rate. Secondary efficacy analyses will include PFS, DOR, and OS. Exploratory analyses will be summarized descriptively and relationships between clinical outcomes and safety may be explored.

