- ^r CT/MRI imaging may include chest, abdomen, and pelvis CT or MRI scans (the same method should be used throughout the study). Brain scans will be performed at baseline if disease is suspected and on study as appropriate to follow disease. CT or MRI scans to be done every 9 weeks (± 7 days) (e.g., Day 1 of Cycles 4, 7, 10, 13, etc.). Tumor assessments should be repeated at the EOT visit if more than 9 weeks have passed since the last evaluation. Patients should have confirmatory scans for response or progression and should remain on treatment if they are receiving clinical benefit (as determined by the Principal Investigator and upon consultation with the Medical Monitor).
- ^s PSMA PET to be performed at selected sites only.
- ^t HPN424 IV will be administered via 1-hour infusion. HPN424 will be administered once weekly (-2 days/+1 day) with a minimum of 4 non-dose days between 2 consecutive doses. Doses are to be calculated based on the patient's baseline (Screening) body weight, not adjusted each cycle for weight at Day 1 of each cycle. Please refer to [Section 5.1.4 Hospitalization and Monitoring](#) for additional instruction on requirements for post-dose monitoring.
- ^u Adverse events (including serious AEs [SAEs]) recorded from signing of informed consent form through the SFU (≥ 28 days [+7 days] after last dose of HPN424).

- ^v C-reactive protein (CRP): at C1D1—predose (-72 h), 5 h (\pm 1 h) after end of infusion (EOI), C1D2—24 h (\pm 1 h) after EOI; C1D8—predose (-24 h); once per cycle (predose [- 24 h] starting with Cycle 2), and when signs of cytokine release syndrome (CRS) are observed.
- ^w 12-Lead ECG: Patients should be resting in a supine or sitting position for \geq 10 minutes prior to electrocardiogram (ECG) collection. Obtain 1 ECG pre-dose at each of the following timepoints: Screening; D1 of each cycle; EOT visit. If cardiac abnormalities are detected or suspected, two additional ECGs must be performed to further evaluate and each reading should be obtained at least 3 minutes apart.
- ^x Pulse oximetry: Within 1 hour prior to each dose.

Table 16 Intravenous Fixed Dosing Regimen: Research Specimen Collection

Cycle	Study Day	Cytokines ^a	Immuno-phenotyping	CTC	PK ^b	Anti-Drug Antibodies
Cycle 1	C1D1-Pre dose	X	X	X	X	X
	C1D1-EOI				X	
	C1D1-2 h Post EOI				X	
	C1D1-5 h Post EOI	X	X		X	
	C1D2	X	X		X	
	C1D3	X	X		X	
	C1D5				X	
	C1D8-Pre dose	X			X	
	C1D8-EOI				X	
	C1D8-5 h Post EOI	X			X	
	C1D15-Pre dose	X		X	X	X
	C1D15-EOI				X	

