	Soft tissue lesions: Progressive disease on CT or MRI by RECIST v1.1	Confirmatory scan required for soft tissue disease progression	Confirmatory scan required for soft tissue disease progression

Abbreviations: CR=complete response, PD=progressive disease, PR=partial response, SD=stable disease, NE=nonevaluable.

- a. Progression detected by bone scan at an unscheduled visit either before Week 9 or between scheduled visits will require a confirmatory scan at least 9 weeks later and should follow confirmation criteria outlined in the table for the next scheduled scan.
- b. Confirmation must occur at the next available scan.
- c. For confirmation, at least 2 of the lesions first identified as new must be present at the next available scan (confirmation scan).

Disease progression in bone must be confirmed at least 9 weeks later, as per PCWG3. See [Table 21](#) below for the timing of confirmatory imaging requirements.

Table 21 Confirmatory Imaging Requirements for Patients with CRPC Based on RECIST v1.1 and PCWG3

Disease Site	Response	Progression ^a
Soft tissue	Must be confirmed at least 9 weeks later	Confirmation required
Bone	Not applicable	Must be confirmed at least 9 weeks later
a. To inform permanent treatment discontinuation		

Radiographic progression-free survival (PFS) is defined as the time from enrollment to documentation of radiographic progression in soft tissue by Investigator's assessment according to RECIST v1.1 ([Table 22](#), [Table 23](#)), in bone by Investigator's assessment according to PCWG3, or death, whichever occurs first.

Table 22 Objective Response Status at Each Evaluation

Target Lesions	Nontarget Disease	New Lesions	Objective Status
CR	CR	No	CR
CR	Non-CR/non-PD	No	PR
CR	Indeterminate or Missing	No	PR
PR	Non-CR/non-PD, indeterminate, or missing	No	PR
SD	Non-CR/non-PD, indeterminate, or missing	No	Stable
Indeterminate or missing	Non-PD	No	Indeterminate
PD	Any	Yes or No, including bone determination	PD
Any	PD	Yes or No	PD
Any	Any	Yes	PD

Abbreviations: CR=complete response, PD=progressive disease, PR=partial response

If there is a protocol deviation and a patient has been enrolled with only nontarget disease, [Table 23](#) will be used.

Table 23 Objective Response Status at Each Evaluation for Patients with Nontarget Disease Only

Nontarget Disease	New Lesions	Objective Status
CR	No	CR
Non-CR/Non-PD	No	Non-CR/Non-PD
Indeterminate	No	Indeterminate
Unequivocal progression	Yes or No	PD
Any	Yes	PD

[figure not shown]

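### SAP 9.1.1 takes best overall response from unconfirmed CR/PR although protocol Table 21 requires confirmation, and SAP 11 declares no change (minor, listings only)

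*SAP*

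**What the plan says.** SAP 9.1.1 defines best overall response (BOR) as the best single assessment on the scale CR > PR > SD > PD > NE, up to documented progression and before any new cancer treatment. It adds: "Confirmation of a response is not required for BOR". SAP 9.1.3 computes duration of response (DOR) only for patients identified as responders and does not define a confirmed responder. SAP 9 says that imaging endpoints are determined by the investigator under PCWG3. SAP 11 says that detail was added but no protocol-specified analysis was changed.

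Protocol 10.8 says that the efficacy analysis "will be based on radiographic response per Prostate Cancer Working Group 3 (PCWG3) criteria" and refers to Appendix 6. In that appendix, the soft-tissue row of Table 21 says under Response that it "must be confirmed at least 9 weeks later". Footnote r in all four schedules of assessments (Appendices 1 to 4) adds: "Patients should have confirmatory scans for response or progression".

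**The concern.** Both rules cannot govern the same derived response. The protocol's version of PCWG3 asks for a second scan at least 9 weeks after a soft-tissue response. The SAP says it follows PCWG3 and then waives that scan. SAP 11 is where a reader looks for departures from the protocol, and it reports none.

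At stake is how Listing 16.2.6.1 (overall efficacy endpoints) would be read. As the derivation stands, a response seen once and lost at the next scan gets the same BOR as one that was confirmed. The change record also matters here because the study is open-label, and SAP version 1.0 (3 March 2023) is dated almost a year after the decision to discontinue (10 March 2022). Nothing in the documents suggests a motive.

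**Working it through.** **1. Does Table 21 govern response?**

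| Place | What it requires |
|---|---|
| Protocol 10.8 | Response per PCWG3, as given in Appendix 6 |
| Appendix 6, Table 21, soft tissue, Response | Confirmation at least 9 weeks later |
| Appendix 6, Table 21, footnote a | "To inform permanent treatment discontinuation"; marked on the Progression header only |
| Appendices 1 to 4, footnote r | Confirmatory scans for response |
| SAP 9 | Imaging endpoints determined under PCWG3 |
| SAP 9.1.1 | No confirmation needed for BOR |
| SAP 11 | No change declared |

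Footnote a does not limit the Response column, so the 9-week rule stands without a qualifier. It is the only text in the protocol on the timing of soft-tissue response confirmation.

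**2. Reach within the SAP outputs (SAP 13.1).**

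- Tables: 6 (14.1.x) + 17 (14.3.2.x) + 1 (14.3.3) + 4 (14.3.4.x) + 1 (14.3.5) + 1 (14.3.6) = 30. There is no 14.2 series, so no table reports efficacy.
- Efficacy listings: 16.2.6.1 to 16.2.6.8 = 8. Going by its title, only 16.2.6.1 would carry the derived endpoints.
- Fields: BOR directly. DOR is an inference: SAP 9.1.3 depends on who is a responder, and the only other responder wording in the SAP's retained text is the reference to non-responders inside the BOR definition.

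**3. Effect on one affected patient.** Inputs: scans every 9 weeks (63 days), each with a ±7-day window (footnote r); durations counted as the difference in dates plus one day, and months as days / 30.4375 (SAP 7.2).

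- Shortest gap between consecutive in-window scans: 63 − 7 − 7 = 49 days.
- Longest gap: 63 + 7 + 7 = 77 days.
- PR on the first scan and PD on the second, plus one day: DOR = 50 to 78 days; 50 / 30.4375 = 1.64 and 78 / 30.4375 = 2.56 months.
- Without the added day: 49 to 77 days; 49 / 30.4375 = 1.61 and 77 / 30.4375 = 2.53 months.

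SAP 7.2 writes the plus-one rule from the first dose date. Applying it from the response date is an assumption, so both ranges are shown. Under SAP 9.1.1 this patient is listed as BOR = PR. Under Table 21 there is no confirmed response and so no confirmed DOR.

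**4. The plan's only response-based figures.** These are the Simon design values (protocol 10.2: 14 then 20 patients, stop on 0 responses, reject the drug on 1 or fewer in total).

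- At ORR 0.01, early termination = 0.99^14 = 0.8687 (stated 0.869).
- Expected size = 14 + 6 × (1 − 0.8687) = 14.79 (stated 14.8).
- Type 1 error = 1 − 0.99^14 − 14 × 0.01 × 0.99^19 = 0.0156 (stated 0.016).
- At ORR 0.15, type 2 error = 0.85^14 + 14 × 0.15 × 0.85^19 = 0.1985 (stated 0.199).

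All four reproduce. The present point does not depend on them, because Part 2 never opened.

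**The case against.** The best defence is that SAP 11 can be read as correct. Protocol 10.8 defines ORR as CR or PR by investigator under PCWG3, and DOR as the "time from the first observed response (CR or PR) to documented disease progression or death due to any cause"; neither mentions confirmation. Table 22 and the CR and PR definitions in Appendix 6 do not mention it either. BOR is not a protocol endpoint, so a rule for it could count as added detail. Where Appendix 6 wants confirmation inside a definition, as for PSA partial response, it writes it there. Appendix 6 is also untidy on other confirmations: bone progression has 9 weeks in Tables 20 and 21 but 6 in Table 24, and Table 20 contradicts itself on soft-tissue progression at Week 9.

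Some of this stands. The departure is from Table 21, reached through the reference in 10.8, and not from the ORR or DOR wording. The DOR effect is only an inference. No listing shell is given, so the content of 16.2.6.1 is read from its title. The waiver itself is disclosed in SAP 9.1.1, and a reader could probably establish confirmation from Listings 16.2.6.2 to 16.2.6.7.

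The rest does not remove the mismatch. Table 22 and the CR/PR definitions give status at one evaluation, whereas BOR is derived across visits, where a confirmation rule operates. Starting DOR at the first observed response fixes a start date and does not cancel Table 21. The inconsistencies about progression do not touch the response rule. Dropping a mandatory confirmation step is a change, whatever the derived variable is called.

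**Conclusion.** The concern holds, with minor severity. SAP 9.1.1 departs from Table 21, and SAP 11 is inaccurate in not saying so. No test, rate, summary table or safety conclusion changes. The reach is one listing, in BOR and, by inference, DOR. The documents give no responder count, so the number of affected patients is unknown and may be zero. The DOR range describes a hypothetical patient whose scans fall in window.

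Confidence is high on the conflict between the texts. The DOR extension rests on reading the responders of SAP 9.1.3 as those with a CR or PR under SAP 9.1.1.

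**What to change.** - **Listing 16.2.6.1:** flag each CR or PR as confirmed or unconfirmed under Table 21 and show the days between the two scans. Derive BOR and DOR on the confirmed basis, with the unconfirmed version alongside. At minimum, footnote the listed BOR and DOR as unconfirmed.
- **SAP 11:** state that the handling of response confirmation in SAP 9.1.1 departs from protocol Table 21.
- **Scan window:** an in-window next scan can fall 49 to 62 days after the first, short of the 63 days Table 21 asks for. If the sponsor accepts such scans as confirmation, SAP 11 should declare that as a sponsor choice.

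The cost is one flag and one day count in one listing (or one footnote), plus one sentence in SAP 11, or two if the scan-window choice is declared. It uses scans already collected and needs no protocol amendment. The price to the sponsor is that some listed responses may become unconfirmed.

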9.1.2 Progression-Free Survival (PFS)

PFS is defined as the time from first dose of study drug to first documentation of disease progression or death due to any cause. Patients who do not experience progressive disease and are alive will be censored at the time of last evaluable tumor assessment. See Section 13.2 for detailed PFS censoring rules.

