7.2 Definitions of Study Day, Durations, Baseline, and Post-Baseline Changes

Study day will be based on the date of administration of the first dose of HPN424 study treatment. Date calculations for any duration outcomes will be defined as follows:

- date of interest – first dose date + 1, when the date of interest is on or after the first dose date
- date of interest – first dose date, when the date of interest is before the first dose date

Study Day 1 is defined as the day the first dose of HPN424 study treatment is administered.

Duration outcomes will generally be reported in days. When necessary to convert to weeks, the duration in days will be divided by 7. When necessary to convert to months, the duration in days will be divided by 30.4375. When necessary to convert to years, the duration in days will be divided by 365.25.

Baseline will be based on the last non-missing value collected before or on the date (and time, if applicable) of the first dose of HPN424 study treatment. Post-baseline values will be those collected after the first dose of study treatment.

Change from baseline is defined as: post-baseline value – baseline value.

Percentage change from baseline is defined as:

$[(\text{post-baseline value} - \text{baseline value}) / \text{baseline value}] \times 100\%$

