13.2 Progression-free Survival Censoring Rules

(Censor for new anti-cancer therapy but not for treatment withdrawals.)

Situation	Date of Progression or Censoring	Outcome
Death before first assessment visit	Date of death	Progressed
No Baseline tumor assessments	Day 1	Censored
Death or progression after more than one missed assessment before switch to other anti-cancer therapy	Date of last radiological assessment of measured lesions	Censored
Progression documented before switch to other anti-cancer therapy	Earliest of the following assessed before switch to other anti-cancer therapy: 
• Date of radiological assessment showing new lesion (if progression is based on new lesion); or• Date of last radiological assessment of measured lesions (if progression is based on increase in sum of measured lesions)	Progressed
Death between adequate assessment visits before switch to other anti-cancer therapy	Date of death	Progressed
Switch to other anti-cancer therapy.	Date of last radiological assessment of measured lesions prior other anti-cancer therapy	Censored
No progression before switch to other anti-cancer therapy	Date of last radiological assessment of measured lesions	Censored

Source: Clinical Trial Endpoints for the Approval of Non-Small Cell Lung Cancer Drugs and Biologics, Appendices C and D

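### SAP PFS rules give a negative time to a patient whose only scan is at screening and who is alive or switches therapy; an undefined term leaves some late deaths open to two outcomes

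*SAP*

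**What the plan says.** SAP 9.1.2 sets the clock: "PFS is defined as the time from first dose of study drug to first documentation of disease progression or death due to any cause". For the rest, "Patients who do not experience progressive disease and are alive will be censored at the time of last evaluable tumor assessment", and the reader is sent to SAP 13.2 for details.

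In SAP 13.2, four rows and the note above the table matter here:
- "No Baseline tumor assessments": censored at Day 1. This is the only row that uses Day 1.
- Patients who switch therapy, and patients with no progression before a switch: censored at the last imaging of the measured lesions.
- "Death before first assessment visit": an event on the date of death.
- "Death or progression after more than one missed assessment before switch to other anti-cancer therapy": censored at the last imaging of the measured lesions.
- The note says to censor for new anti-cancer therapy but not for treatment withdrawal.

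SAP 7.2 supplies the arithmetic. Its scope is wide: "Date calculations for any duration outcomes will be defined as follows". For dates before treatment the rule is "date of interest – first dose date, when the date of interest is before the first dose date", which is below zero by construction.

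**The concern.** The rules protect the wrong patient. Someone with no baseline scan is placed at Day 1. Someone with a valid baseline scan and nothing after it is sent back to a date before the clock started. A PFS time below zero is impossible, and survival software will usually drop or reject such a record.

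The death rows raise a second question. The first has no stated time limit, and the term it relies on is not defined as a scheduled visit or as an attended one. A patient who is never scanned on study and dies late may fit both rows, with opposite outcomes and no stated order of precedence.

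At stake is whether the PFS value derived for patients without an on-study scan is usable and reproducible, or depends on what the programmer decides.

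**Working it through.** The plan states no PFS time, event count or power, so there is no figure to reproduce. The check applies the plan's date rules as written.

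**Inputs**
- Origin F = date of first dose (SAP 9.1.2).
- Duration for a date D (SAP 7.2): D - F + 1 if D is on or after F; D - F if D is earlier. Months = days / 30.4375.
- Screening runs from Day -28 to Day -1 (Protocol 8.1). Baseline scans fall within 28 days before treatment (Protocol Appendix 6). Imaging at screening is required (Protocol 6.20).
- On-study scans are due every 9 weeks, plus or minus 7 days, counted from C1D1 (footnotes to the Schedules of Assessments).

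**Step 1. Alive without progression, screening scan only.** The last assessment is the screening scan.

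| Scan | Calculation | PFS, days | PFS, months |
|---|---|---|---|
| 28 days before first dose | D - F | -28 | -28 / 30.4375 = -0.92 |
| 14 days before | D - F | -14 | -0.46 |
| 1 day before | D - F | -1 | -0.03 |
| Day of first dose | 0 + 1 | 1 | 0.03 |
| No baseline scan (13.2, Day 1) | 0 + 1 | 1 | 0.03 |

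**Step 2. Switch to another anti-cancer therapy, screening scan only.** The switch row uses the last imaging before the new therapy. That is again the screening scan, so the result is again -28 to -1 days.

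**Step 3. Can the pattern occur?** Yes. The first on-study scan is at Week 9, and Protocol 6.24 and 8.3 allow the End of Treatment scan to be skipped if imaging was done within 9 weeks. A patient scanned 14 days before first dose who stops on Day 30 is 14 + 29 = 43 days from that scan, which is under 63.

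**Step 4. Late death with no on-study scan.** Week 9 is Day 7 x 9 + 1 = 64 (window 57 to 71). Week 18 is Day 7 x 18 + 1 = 127 (window 120 to 134). Take a screening scan 14 days before first dose, both on-study scans missed, no new therapy, and death on Day 150.
- *If the visit means the first scan actually done:* the early-death row gives an event at 150 days (150 / 30.4375 = 4.93 months). The missed-assessment row gives censoring at -14 days (-0.46 months). Both rows fit.
- *If the visit means the scheduled Week 9 assessment:* a death before it comes no later than Day 71, and a second scan cannot have been missed before Day 120. The rows cannot overlap. This patient falls under the missed-assessment row only, with one outcome, but the censoring date is still -14 days.

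**The case against.** The strongest objection is materiality. The study was stopped in Part 1, PFS is struck through in SAP 4.4, SAP 9 confines efficacy to by-patient listings, and no p-values are planned. A listed value of -14 would be visible, and the scan, death and survival listings would let a reader recover the right one. All of this stands. It sets the severity but does not remove the defect, because 9.1.2 and 13.2 remain in force and SAP 6 and 7.1 call for derived variables in the listings.

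It can also be said that an evaluable assessment obviously means one made on treatment. The text does not say so. SAP 9.1.1 restricts best overall response to assessments after first dose and says what to do when there are none. The PFS section does neither.

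Some stronger readings are tempting and are not supported:
- *Everyone who leaves before Week 9 is affected.* A patient who dies before Week 9 without a switch gets a valid event date. Protocol 6.20 continues imaging after treatment stops (Protocol 6.18 is narrower), so leaving treatment early does not by itself mean no scan.
- *The SAP plainly contradicts itself on late deaths.* It does so only if the visit means the scan actually done. The word visit, and the counting of missed assessments, fit a schedule at least as well.
- *Deaths after new therapy are counted as events because the early-death row has no therapy clause.* The note above the table and the separate switch row largely cover this.
- *A PFS estimate is biased.* None is planned in the SAP.

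**Conclusion.** The negative-time defect is established on the literal text: -28 to -1 days for a patient with only a screening scan who is alive without progression or who switches therapy. The same date reaches an unscanned late death whenever the missed-assessment row is applied. The overlap between the two death rows is conditional on how an undefined term is read, so it should be treated as a need for a definition rather than as a proven contradiction.

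Severity is low. No planned estimate or decision changes. The effect is on derived PFS values in Listing 16.2.6.1, and on any later PFS summary built with these rules, such as the Kaplan-Meier description in Protocol 10.8.

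This rests on two assumptions. The scan is taken before the day of first dose (a same-day scan gives +1). And Listing 16.2.6.1, titled as the overall efficacy endpoints, carries the derived PFS time. The documents do not say how many patients lack a post-baseline scan, so the number affected is unknown.

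**What to change.** 1. Add a row to SAP 13.2: no post-baseline tumor assessment, and alive or switched to other anti-cancer therapy, is censored at Day 1.
2. State that no censoring date may precede Day 1. This also covers a death censored under the missed-assessment row when the only scan is at screening.
3. Define the first assessment visit as the scheduled Week 9 assessment, or state which of the two death rows takes precedence. If the scheduled definition is chosen, say also that a death after only the Week 9 scan was missed is an event at death, as the definition in 9.1.2 already implies.

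The cost is a few lines of SAP text and code, with no new data. If the SAP is not to be amended, the same rules can be applied in the derivation and described in the study report, as SAP 11 provides for deviations from the plan.
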